### 3.3. C. Research Design and Methods: R61 Phase.

**3.3. C.1. Overview.** The R61 Phase is designed to clarify engagement of the attention allocation target, to optimize dosage of GC-MRT (RCT comparing 8 vs. 12 sessions), and to explore whether the treatment engages two processes influencing attention allocation: disengagement from threat, and social reward.

**3.3. C.2. R61 Method: Patients:** The goal is to enroll a sample with clinically significant SAD, using few exclusion criteria to maximize generalizability. Patients will be obtained by clinical referral and recruitment notices posted online and locally. Forty adults age 18-60 with clinically significant SAD, as assessed by MINI structured interview and self-rated Liebowitz Social Anxiety Scale (LSAS-SR) total  $\geq 50$ , will enter the study after psychiatric clinical evaluation, including and Hamilton Rating Scale for Depression (HRSD). The LSAS cutoff score was chosen for optimal balance between diagnostic specificity and sensitivity for SAD. Key exclusion criteria will be at least moderately severe depression (HDRS 17-item score  $>20$ ), indicating greater need for non-experimental treatment; substance use disorder in the past 30 days (other than nicotine, or mild alcohol or cannabis abuse); bipolar or psychotic disorders; acute suicidal ideation (assessed by Columbia Suicide Severity Rating scale, CSSR); other unstable psychiatric, neurological, or medical conditions that could interfere with study participation or interpretation of outcomes; contraindication to MRI. (see Human Subjects for details).

[figure not shown]
The self-rated version of the LSAS will be used only at screening for eligibility assessment. The clinician-rated LSAS will be the primary outcome measure, assessed at baseline, during treatment, and post-treatment. Using the self-rated LSAS at screening avoids the bias that reportedly can occur when the primary outcome measure is the basis for an entry cutoff criterion, as raters could feel pressured to maximize baseline scores to meet the cutoff, thus distorting outcomes.

**3.3. C.3 R61 Intervention:** Patients will be randomized to 8 biweekly sessions of GC-MRT over 4 weeks vs. 12 sessions of GC-MRT over 8 weeks (8 biweekly, then 4 weekly), using GC-MRT as described above in the preliminary study, but without a control treatment – all R61 patients will receive active GC-MRT.

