corresponding to  $d = 0.34$ , while with  $r = 0.2$ , the minimal detectable effect size is  $f = 0.23$  or  $d = 0.45$ . In either case, the power for  $d = 0.68$  will be  $>99\%$ .

**Aim 2: Hypothesis 2:** *Eight weeks after starting treatment, mean Liebowitz Social Anxiety Scale (LSAS) total score will be significantly lower in the 8-week treatment group than in the 4-week group.* We will use a t-test for the change score at 8 weeks after starting treatment for completers. We will also compare groups on % dwell time at last session but do not expect a group difference. Power Analysis. We do not have preliminary data for the 8-week dose of treatment. For the two-group t-test, with  $n=20$  per group enrolled, and 18 per group completers (10% dropout), we will have 80% power to detect an effect of size  $d=0.96$  or larger. Thus we will be able to detect large effect sizes for the dosage difference. However, dose selection for the R33 will not require statistically significant superiority (see criterion for selecting dose, below).

**Aim 3 (Exploratory):** (See below for processing MRI and tasks data) We will test the association between change in attention control and reward processing and change in % dwell time by Pearson correlation coefficients. *We will also explore predictors of target engagement (baseline attention allocation and neural activation), to advance personalized treatment.* We will fit mixed effect regression models as described in Hyp 1, with repeatedly measured reduction in % dwell time as outcomes, with the predictors listed above.

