Whole-brain 2X2 voxel-wise Analysis of Variance (ANOVA) will be conducted to evaluate main effects of Time (pre- and post- treatment), Stimuli type (match faces and match shapes), and Time by Emotion interactions for only angry faces at the R61 phase for each dose group. For the R33 phase, whole-brain 2X2X2 ANOVA will be conducted to evaluate main effects of Group (active and control), Time (pre- and post-treatment), and Stimuli type (match faces and match shapes), and Group by Time by Stimuli type interactions for only angry faces. A stringent threshold for significance will be set at  $p < 0.05$ , corrected for multiple comparisons across the entire brain using a FWE with a cluster size of at least 10 contiguous voxels. Significant main effects and interactions will be tested by post hoc t-tests to clarify the direction of effects.

**Reward Task fMRI:** During individual-level analyses, functional activation maps of the reward task will be computed by regressing each voxel's fMRI response time course onto an ideal response function consisting of a canonical hemodynamic response function convolved with the time-series of each response type of the entire duration of anticipation and outcome phases of the task. In addition, six movement parameters obtained during realignment were included in the model as regressors to account for motion-related effects in BOLD signal.

A whole-brain voxel-wise two-way t-test model will be conducted with two time points (pre-, post-treatment) in the R61 phase for each dose group. It will be applied separately for the anticipatory and outcome phases of the task, and each outcome will be modeled against an implicit baseline (the anticipatory phase models only 'potential win' trials and the outcome phase models only successful 'potential win' trials). For the R33 phase, whole-brain 2X2 ANOVA will be conducted to evaluate main effects of Group (active and control), and Time (pre- and post- treatment), and Group by Time interactions. Significant clusters will be further evaluated by extracting subject- and condition-specific signal intensity coefficients to evaluate simple effects.

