**Resting State Analysis:** We will apply probabilistic independent component analysis (PICA) using the Multivariate Exploratory Linear Decomposition into Independent Components (MELODIC) toolbox of the FMRIB Software Library (FSL) package. A temporal concatenation tool in MELODIC will derive group level components across all subjects. The number of dimensions will be estimated using the Laplace approximation to the Bayesian evidence of the model order. The whitened observations will be decomposed into sets of vectors that describe signal variation across the temporal domain (time-courses) and across the spatial domain (maps) by optimizing for non-Gaussian spatial source distributions using a fixed-point iteration technique. These functional connectivity component maps will be standardized into z statistic images via a normalized mixture model fit, thresholded at  $z > 5$ . Networks of interests including the reward network, salience network, executive control network, and the default mode network will be identified by visual inspection. The between-subject analysis will be carried out using dual regression, a regression technique that back-reconstructs each group level component map at the individual subject level).

Voxel-wise two-sample t-tests will be used to assess statistically significant differences in FC between the groups using a 5000 non-parametric permutation testing. A threshold-free cluster enhanced technique will control for multiple comparisons. This method allows detecting significant clusters without having to define cluster size or the number of clusters prior to analysis. Resulting statistical maps will be thresholded at  $p < 0.05$  family-wise error (FWE)-corrected for multiple comparisons. The Harvard-Oxford atlases incorporated in FSL will be used to identify the anatomical regions of the resulting PICA maps.

**Attention Control Task behavioral analysis:** The accuracy of trials and the RTs for accurate trials will be recorded. Behavioral data will be submitted to a 2 Time (pre-, post- treatment) x 2 Stimuli type (match faces and match shapes) ANOVA for angry faces only in the R61 phase for each dose group. For the R33 phase,

behavioral data will be submitted to a 2 Group (active and control) X 2 Time (pre-, post- treatment) x 2 Stimuli type (match faces and match shapes) ANOVA for angry faces only. Significant main effects and interactions will be followed up with two-tailed t-tests,  $p < 0.05$ .

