Reward Task behavioral analysis: Valence, arousal ratings of faces, and reaction times (RTs) for both potential reward and non-potential reward trials will be recorded. RTs, valence and arousal ratings of faces will be submitted to 2-way t-tests (pre-, post-treatment) for the R61 phase for each dose group. For the R33 phase, a two-way ANOVA will be conducted to test main effects of Group (control and treatment), Time (pre- and post-treatment), and Group by Time interactions. Interactions will be followed up with two-tailed t-tests,  $p < 0.05$ .

Social Probabilistic Reward Task: Response bias ( $\log b$ ; primary variable) and discriminability ( $\log d$ ; control variable) will be computed following prior procedures. using the following formulas:

$$\log b = \frac{1}{2} \log \left( \frac{Rich_{correct} * Lean_{incorrect}}{Rich_{incorrect} * Lean_{correct}} \right) \quad \log d = \frac{1}{2} \log \left( \frac{Rich_{correct} * Lean_{correct}}{Rich_{incorrect} * Lean_{incorrect}} \right)$$

Response bias indexes the systematic preference for the response paired with the more frequent reward ("rich stimulus"), or the extent to which behavior is modulated by reinforcement history. A high response bias emerges when subjects show high rates of correct identification (hits) for the rich stimulus and high miss rates for the lean stimulus (i.e., the stimulus associated with less frequent rewards). To examine general task performance, secondary analyses will consider hit rates scores (% correct responses), RT, and discriminability. Discriminability assesses the subjects' ability to perceptually distinguish between the two stimuli, and thus can be used as a proxy of task difficulty.

Data Reduction: The main dependent variable for the PRT will be Reward Learning, operationalized as the increase in response bias during the final block relative to the first block [Reward Learning =  $\Delta$ Response Bias = Response Bias(Block 3) - Response Bias(Block 1)].  $\Delta$ Response Bias is consistently positive in healthy subjects, and we selected this as the main outcome measure because lower values of it have been linked to current and future anhedonic symptoms and reward-related cortico-striatal activation.

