## PROTECTION OF HUMAN SUBJECTS

### a. Human Subjects Involvement, Characteristics, and Design

#### **Overview:**

We anticipate recruiting and entering 40 adults, age 18-60, with social anxiety disorder. They will complete diagnostic evaluations and begin full testing, including procedures of behavioral tasks, MRI, and 8 or 12 sessions of computer-based treatment. We estimate that overall 10% of participants will not complete all procedures due to noncompliance or movement artifacts.

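### The exploratory R61 pre-post tests of the attention-control and social-incentive tasks are specified only within each dose group of about 18, with no pooled Time or Dose-by-Time test

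*Combined protocol and SAP*

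**What the plan says.** Section 3.3. C.5 specifies four R61 analyses by dose group:

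- **Attention Control Task fMRI:** a Time by Stimuli type ANOVA, "for only angry faces at the R61 phase for each dose group".
- **Reward Task fMRI:** a voxel-wise t-test with "two time points (pre-, post-treatment) in the R61 phase for each dose group".
- **Attention Control Task behavioral analysis:** a Time by Stimuli type "ANOVA for angry faces only in the R61 phase for each dose group".
- **Reward Task behavioral analysis:** reaction times and face ratings go into "2-way t-tests (pre-, post-treatment) for the R61 phase for each dose group".

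For R33 the same paragraphs put both arms into one model. The reward-task imaging model, for instance, has "main effects of Group (active and control), and Time (pre- and post- treatment), and Group by Time interactions".

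The R61 purpose is stated for the treatment as a whole. Section 3.3. C.1 says the phase will "explore whether the treatment engages two processes influencing attention allocation", and section 3.3. C.3 makes clear that there is no control arm.

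Other parts of section 3.3. C.5 are not split by dose. Hypothesis 1 (% dwell time) is explicitly pooled. The Aim 3 correlations state no split, and the Aim 3 predictor models follow the Hypothesis 1 model. Resting-state components are derived from all subjects and compared between groups, with no phase named. The reward-learning task has no per-dose rule.

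**The concern.** Whether the treatment changes attention control or social reward processing is one question, and both R61 arms carry information on it. As written, it is asked twice, each time on half the patients, and the plan does not say how the two answers combine into one. Two things follow. First, each test is less sensitive than the data allow. Second, the reader is left with two significance statements side by side and no direct test of whether the arms differ, so a chance difference between them could be mistaken for a dose effect. At stake is how well R61 can inform the process question, which the plan labels exploratory.

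**Working it through.** **Inputs**

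- Completers: the Aim 2 power analysis gives 20 enrolled per group "and 18 per group completers (10% dropout), we will have 80% power to detect an effect of size" 0.96 or larger. So 20 x 0.9 = 18 per arm and 36 in total.
- Loss to scan quality: the Overview under Protection of Human Subjects estimates that "overall 10% of participants will not complete all procedures due to noncompliance or movement artifacts", so the 10% already covers movement.
- Effect sizes: the documents give none for the imaging or task measures. I borrow d = 0.48 and d = 0.68 from the % dwell time power analysis (Aim 1), purely as illustrative values.
- Alpha: 0.05, taken as two-sided because the Aim 1 text does not state sidedness.

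**Formulas**

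- Paired t-test: noncentral t with n - 1 degrees of freedom and noncentrality d x sqrt(n). In a 2 x 2 within-subject ANOVA, the Time-by-Stimuli term is equivalent to a paired t-test on the difference of differences, so the same formula serves both tasks.
- Two-group t-test on change: 2n - 2 degrees of freedom and noncentrality d x sqrt(n/2).

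**Step 1: reproduce the plan's figures**

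- Paired, n = 36, d = 0.68: noncentrality 0.68 x 6 = 4.08, power 97.8% (plan: 98%).
- Paired, n = 36: smallest d with 80% power is 0.480 (plan: 0.48).
- Two-group, 18 per arm: smallest d with 80% power is 0.961 (plan: 0.96).

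**Step 2: cost of splitting**

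| | One arm, n = 18 | Pooled, n = 36 |
|---|---|---|
| Detectable d, 80% power | 0.70 | 0.48 |
| Power at d = 0.48 | 48.4% | 80.0% |
| Power at d = 0.68 | 77.6% | 97.8% |

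The detectable effect grows by a factor of 0.701 / 0.480 = 1.46. With 16 to 20 usable patients per arm, the within-arm figure runs from 0.75 to 0.66. The matching pooled figure (32 to 40) runs from 0.51 to 0.45.

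**Step 3: the pooled Time term in a Dose x Time model**

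With 36 completers and 34 degrees of freedom, the detectable d is 0.48, and power is 79.9% at d = 0.48 and 97.7% at d = 0.68. Including Dose costs almost nothing.

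**Step 4: what two separate tests show when the arms do not differ**

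Suppose the true effect is the same in both arms and p is the power within one arm.

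- Exactly one arm significant, 2p(1 - p): at d = 0.48, 2 x 0.484 x 0.516 = 0.50. At d = 0.68, 2 x 0.776 x 0.224 = 0.35.
- At least one arm significant, 1 - (1 - p)^2: at d = 0.48, 1 - 0.516^2 = 0.73. The false-positive rate of that rule is 1 - 0.95^2 = 9.75%. So even a lenient either-arm rule has less power than the pooled test (73% against 80%), at nearly twice the error rate.

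**Step 5: what the Dose-by-Time term can deliver**

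It is a two-group comparison of change scores, 18 against 18. From Step 1 it has 80% power only for d of about 0.96, in SD units of the change score.

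**The case against.** The case for leaving the plan alone has real weight. The arms differ in exposure: section 3.3. C.3 gives 8 sessions over 4 weeks against 12 over 8 weeks. Only one dose goes into R33, so a dose-specific pre-post estimate is a legitimate exploratory target, and a pooled effect averages over two different courses. The R33 parallel is also imperfect. There the Group factor is active against control, so Group-by-Time is the treatment effect; in R61 both arms are active. These points stand. They are reasons to keep the per-dose estimates, but they do not justify having no pooled test when the stated question concerns the treatment.

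A reader might infer more than the documents support:

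- **That R61 engagement testing as a whole is split.** It is not. The primary % dwell time test is pooled, and the Aim 3 correlations and predictor models, resting state and the reward-learning task carry no per-dose rule. The Aim 3 analyses do not fill the gap, though: a correlation between changes does not test whether the mean changed.
- **That the plan compares doses by contrasting significance.** No section proposes this. Dose is compared directly on LSAS change and on last-session % dwell time under Aim 2. The risk lies in how the per-dose results might later be read.
- **That an R61 decision is weakened.** The Go-Nogo and dose-selection criteria use % dwell time and LSAS only.
- **That the figures above are the power of the imaging analysis.** They are not. The attention-task fMRI paragraph sets a whole-brain FWE-corrected threshold with a minimum cluster size, and no effect size is given for any of these measures.

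**Conclusion.** The point holds as a minor improvement to four exploratory analyses: EFSAT and Social Incentive Delay, each in fMRI and behavioural form. They are specified only within dose groups of about 18, with neither a pooled Time test nor a Dose-by-Time test, although the question concerns the treatment and every patient receives it. At two-sided 0.05 and 80% power, splitting raises the detectable paired effect from 0.48 to 0.70. This assumes 10% loss spread evenly over the arms and illustrates only the halving of n. With an identical true effect of 0.48 in both arms, exactly one arm would be significant about half the time, so per-dose significance should not be read as evidence on dose.

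**What to change.** In section 3.3. C.5, replace the four R61 per-dose specifications with one model per task and modality: Dose (between) x Time, adding Stimuli type for EFSAT. State that:

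- process engagement is read from the pooled Time term (Time-by-Stimuli type for EFSAT);
- per-dose estimates are reported as follow-up, with confidence intervals for the behavioural measures;
- any statement about dose rests on the Dose-by-Time term, with a note that 18 per arm gives 80% power only for d of about 0.96 even at 0.05, and less sensitivity under whole-brain correction. A non-significant interaction is therefore not evidence that the doses are equal.

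The cost is SAP wording: the scans, tasks and patients are the same, and no per-dose result is lost. There are two downsides. The model assumes a common error variance in the two arms, and the pooled effect averages over two exposures. The second should be said when the result is reported.

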### 3.3. C.4 Assessments :

These will include eye tracking of attention allocation during GC-MRT, self-ratings, clinician ratings (by an independent evaluator blind to GC-MRT dose assignment and scheduling of GC-MRT sessions), computer-based behavioral tasks, and MRI. Attention allocation will be assessed at every GC-MRT session. MRI assessments and behavioral tasks will be conducted pre- and post-treatment. All other outcome assessments will be conducted at baseline and at weeks 2, 4, and 8, and 3 months later (3-month follow-up).

**3.3. C.4.a. Primary Outcome Assessment for Target of Attention Allocation:** The primary outcome measure will be defined as % dwell time on threat faces (dwell time on threat faces/dwell time on all faces), derived from eye-tracking data obtained throughout each treatment session. Fixations will be defined as  $\geq 100$  ms of stable fixation within  $1^\circ$  visual angle. For each matrix we will define two Areas of Interest (AOI's), one of the eight disgust facial expressions (i.e., the threat AOI) and one of the eight neutral facial expressions (the neutral AOI). Attention allocation to threat will be measured by computing total dwell time in milliseconds per defined AOI and calculating the proportion of dwell time on the threat AOI relative to total dwell time on both AOI's, thus reflecting gaze allocation to threat stimuli. Percentage of dwell time on threat AOI across the 30 presented matrices for each session will be averaged for a final score of attention allocation to threat per session. As in the pilot study, to derive baseline % dwell time we will average the percentage of dwell time on threat AOI during the first five matrices presented in Session 1, as gaze-contingency learning has been shown to be minimal at this early stage.

**3.3. C.4.b. fMRI Tasks:** Patients will complete MRI twice (pre-treatment and post-treatment) using tasks that have been previously shown to differentiate SAD from control participants. Resting state data will be obtained for 15 minutes prior to task completion.

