**Hypothesis 4:** *After GC-MRT, change in % dwell time post-treatment will be significantly associated with improvement in LSAS and QLESQ totals at post-treatment and at 3-month follow-up.* We will calculate Pearson correlation coefficients between % dwell time reduction and LSAS reduction, and, separately, for % dwell time and QLESQ reductions. Power Analysis. From our preliminary data analysis, the expected correlation coefficient for the reduction in % dwell time and reduction in LSAS will be  $r > 0.32$ . With  $n = 80$  subjects and 10% dropout, we will have 80% power to detect a Pearson correlation of  $r = 0.32$  at the 0.05 level.

**Aim 5 (Exploratory):** *To assess whether attention control and reward processing predict symptom change (using same assessment methods as in Aim 3), with fMRI done pre- and post-treatment in a subset ( $n=60$ ).* We will fit regression models, with LSAS change relative to baseline as outcome, and with the baseline predictors listed above as fixed effects, Moderation relationships of treatment effect for the baseline predictors will be explored by including interaction terms with randomization group. We will test the association between change in attention control and reward processing and change in symptoms by Pearson correlation coefficients.

fMRI Data Acquisition: Prior to scanning, patients will practice all tasks and gain familiarity with the scanning environment. Foam pads securing patients in the head coil will limit head movement during data acquisition. The MRI component will last approximately one hour and 15 minutes, using a 3T General Electric MR750 (GE Medical Systems, Waukesha, WI, USA) located in NYSPI, and equipped with a 32 channel receive-only head coil. At the beginning of each session, 15 minutes resting state data will be collected to explore connectivity

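### The resting-state analysis compares groups only, with no pre-post element: in R61 it cannot detect a connectivity change shared by both doses, and in R33 use of the baseline scan is not specified

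*Combined protocol and SAP*

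**What the plan says.** Section 3.3. C.4.b schedules two MRI sessions per patient, one before and one after treatment, and adds: "Resting state data will be obtained for 15 minutes prior to task completion". The fMRI Data Acquisition paragraph in section 3.3. C.5 repeats this: "At the beginning of each session, 15 minutes resting state data will be collected to explore connectivity", in reward and attention-control regions.

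The Resting State Analysis paragraph in section 3.3. C.5 derives group components by independent component analysis and then states: "The between-subject analysis will be carried out using dual regression". One test follows: "Voxel-wise two-sample t-tests will be used to assess statistically significant differences in FC between the groups", with 5000 permutations, threshold-free cluster enhancement (TFCE) and a family-wise error (FWE) corrected threshold of 0.05. The paragraph does not say which scan or map enters the test, which groups are meant, or whether R61 and R33 differ.

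Section 3.3. C.3 states that every R61 patient receives active GC-MRT; the two arms differ only in dose. Section 3.3. C.1 gives one purpose of R61 as to "explore whether the treatment engages two processes influencing attention allocation: disengagement from threat, and social reward".

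**The concern.** Two scans per patient are useful mainly because they allow each patient to be compared with himself or herself. A two-sample test between groups does not do that unless it is given change maps or a baseline covariate, and the plan mentions neither.

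The gap matters most in R61. With no untreated arm, the between-group contrast is a dose contrast. If GC-MRT alters connectivity to a similar degree at both doses, the planned test has nothing to find, and the scans would be reported as showing no difference although patients had changed. In R33 the matter is one of precision and of an analyst's choice left open: the result depends on which maps are used, and that is not fixed in advance.

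**Working it through.** **Step 1. Compare the analyses in section 3.3. C.5.**

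| Analysis | R61 | R33 |
|---|---|---|
| Attention-task fMRI | Time by Stimuli type, each dose group | Group, Time, Stimuli type |
| Reward-task fMRI | Pre vs post, each dose group | Group, Time, Group by Time |
| Attention-task behavior | Time by Stimuli type, each dose group | Group, Time, Stimuli type |
| Reward-task behavior | Pre vs post, each dose group | Group, Time, Group by Time |
| Social Probabilistic Reward Task | No inferential model stated | No inferential model stated |
| Resting state | Two-sample test between groups, phase not distinguished | Same sentence |

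The first four rows name Time and separate the two phases. The resting-state row does neither.

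**Step 2. Check the calculation against stated figures.** No power or effect size is given for resting state, so there is no figure to reproduce. The nearest stated figures do reproduce. For Aim 2 (18 per group, d = 0.96, stated 80% power), a noncentral-t calculation gives 79.9%, with a minimum detectable d of 0.961. For the Hypothesis 1 completer analysis (40 less 10% = 36, d = 0.48), the paired test gives 80.0%.

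**Step 3. R61.** Let both arms share a pre-treatment mean m (by randomization) and a change c.
- Post-treatment maps: expected difference = (m + c) - (m + c) = 0.
- Change maps: c - c = 0.
- Pre-treatment maps: m - m = 0.
- Average of the two scans: (m + c/2) - (m + c/2) = 0.

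The between-group test therefore rejects only at its alpha. A single-measure simulation was run with 20,000 runs, two-sided alpha 0.05, 18 per arm, a shared change of d = 0.48 in change-SD units, and pre-post correlation r of 0.3, 0.5 and 0.7. The two-sample test rejected in 4.8% to 5.2% of runs across all four inputs. The paired test on all 36 rejected in 80.0% to 80.3%. The value d = 0.48 is borrowed from the % dwell time power statement and is an assumption here.

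**Step 4. R33 precision.** Assume equal pre and post variances and a linear relation with correlation r, which the documents do not give. Relative to a post-only comparison, the residual variance is 1 - r² with the baseline map as covariate, and 2(1 - r) for post-minus-pre maps.

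| r | Post-only | Baseline covariate, 1 - r² | Change maps, 2(1 - r) |
|---|---|---|---|
| 0.4 | 1 | 0.84 | 1.20 |
| 0.5 | 1 | 0.75 | 1.00 |
| 0.6 | 1 | 0.64 | 0.80 |
| 0.7 | 1 | 0.51 | 0.60 |

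The covariate cuts variance by 16% to 49% over this range. Change maps are less precise than post-only when r is below 0.5. The covariate is never worse than change maps, because (1 - r²) / [2(1 - r)] = (1 + r)/2, which is at most 1.

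**Step 5. R33 dependence on the input map.** The MRI subset is 60 (Aim 5). Less 10%, and assuming equal allocation, that is 54, or 27 per arm. With an assumed change of d = 0.74 in the active arm (borrowed from the QLESQ power statement) and none in control, rejection rates were:

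| Input map | r = 0.3 | r = 0.5 | r = 0.7 |
|---|---|---|---|
| Pre-treatment | 5.2% | 4.8% | 5.0% |
| Average of both scans | 50.2% | 33.7% | 19.6% |
| Post-treatment | 88.6% | 76.0% | 54.2% |
| Change | 76.0% | 75.7% | 76.6% |

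The effect is fixed in change-SD units, so the raw effect shrinks as r rises. The crossover of post-only and change maps near r = 0.5 agrees with Step 4. Steps 3 and 5 illustrate one measure at uncorrected alpha; they are not estimates of whole-brain power.

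**The case against.** The strongest reply is that the paragraph leaves the input map open and does not fix a defective test. A two-sample test on post-minus-pre maps is the Group by Time test, and a post-treatment comparison of randomized R33 arms is a valid test of treatment effect. A reader might infer that the planned test can show no treatment effect in either phase; for R33 the documents do not support that. This part of the reply stands. It does not help R61, where change maps still test only a dose difference.

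Three other inferences go too far:
- **Chance baseline differences in R33 reported as treatment effects.** For a post-only comparison of randomized arms this is ordinary type I error, held by the FWE-corrected permutation threshold. Ignoring the baseline costs precision; it does not bias the comparison.
- **Both scans of a patient entered as independent observations.** The text describes a between-subject analysis with maps reconstructed for each subject, which weighs against this reading.
- **R61 left with no means of studying engagement.** The two processes named in section 3.3. C.1 are also assessed by the attention-control and social reward tasks, whose fMRI analyses have pre-post contrasts within each dose group.

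Aims 3 and 5 plan correlations of change in attention control and reward processing, and one might read connectivity into them. It is not named there, and a correlation of changes would not test whether mean connectivity changed.

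Finally, the measure carries little weight in the plan: no hypothesis, power statement or decision rule uses it. That limits the importance of the point but does not answer it.

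**Conclusion.** The point holds in limited form. For R61 it follows from the design and needs no assumed figure: both arms are treated, so the stated between-group test cannot detect a connectivity change common to both doses on any input map. The contrast of about 5% with about 80% rests on the assumed d = 0.48 and on treating connectivity as a single measure.

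For R33 the stated test can be valid, but its input is unspecified. If it is post-only, it gives up a variance reduction of 16% to 49%, for an assumed r of 0.4 to 0.7 with equal variances and a linear relation. That gain belongs to covariate adjustment and does not carry over to simple change maps.

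The omission is particular to resting state when set against the attention-task and reward-task analyses. It should not be described as the only analysis without Time, because the Social Probabilistic Reward Task has no stated model either. The consequence is confined to an exploratory measure; the primary outcomes, the Go-Nogo criterion and dose selection do not depend on it. The change is worth making because it is cheap and uses scans already planned.

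**What to change.** Rewrite the Resting State Analysis paragraph by phase, naming the maps and groups.

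- **R61:** test within-patient post-minus-pre dual-regression maps with a one-sample sign-flip permutation, either pooled over all patients or within each dose group as in the task analyses. Report the dose difference in change maps as secondary. Because R61 has no control arm, describe the result as change over the treatment period; the R61 task contrasts carry the same limit.
- **R33:** compare post-treatment maps between groups with each patient's pre-treatment map as a voxel-wise covariate. Prefer this to simple change maps, which are less precise than post-only when r is below 0.5.
- **Both phases:** keep the 5000 permutations, TFCE and the FWE-corrected 0.05 threshold, and state whether both scans enter the group component step.

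The cost is SAP wording and a different design matrix, with no added scanning. The downside is that patients without a usable pre and post scan pair leave these analyses, so their number should be reported by group.
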